- Exposure levels to Second Hand Smoke (SHS) in smoking areas provided by Bars Casinos and Bingo halls etc.

Study Design

Population:

The study population will consist of 30 Asthmatic and 30 Chronic Obstructive Pulmonary Disease (COPD) subjects to be recruited through the European Lung Foundation (ELF) in Hungary Spain and Ireland. (20 subjects in each country)

Inclusion criteria for each patient group:

Confirmed [name] COPD patients

- Current or ex-smokers.
- Fully ambulatory.
- Frequent smoking areas*
- Between 50yrs and 70yrs

Confirmed [name] patients

- Fully ambulatory
- Frequent smoking areas
- Over 18yrs

*Irish law has defined an outdoor smoking area as: A place or premises, or part of a place or premises that, is wholly uncovered by any roof, fixed or mobile. An out door place or premises that is covered by a roof, so long as not more than 50% of the perimeter (outside) is covered by a wall, windows, gate or similar.

Exclusion criteria:

- Under 18yrs
- On Oxygen therapy
- Never smokers in COPD patient group
- Undergoing treatment for acute exacerbations.
- Pregnant women

Primary Endpoints:

- To monitor personal exposure to SHS in areas exempted from legislation in pubs, bars and casinos etc. using novel monitoring technologies.
- To simultaneously monitor the respiratory effects as indicated by changes in respiratory rate and flow and activity levels.

Secondary Endpoints

- Any increase in medication usage
- Unscheduled Primary Care /Hospital visits
- Breath Carbon Monoxide (CO) monitoring pre and post study
- Spirometry pre and post exposure

Ethics:

Ethical approval will be sought from DIT Ethics Committee prior to beginning of the project. All documentation relating to the project will be provided for ethical review. There are no perceived Ethical issues as patients will be fully informed and there will be no intervention other than monitoring. It was considered that requesting subjects to go into outside smoking areas might be a problem so only subjects who already frequent such areas will be recruited.

All participants will be provided with a patient information leaflet and asked to sign an informed consent form. (Appendix 1)

Methodology:

Recruitment

Relevant patient organisations will be identified in each country through European Lung Foundation (ELF) ([name]) and project partners.

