Each patient will visit the centre on 2 occasions the first at enrolment and training in use of equipment, this should be at least 2 to 4 hours prior to exposure. The second will be at least 24hrs post exposure to secondhand smoke at, at least one outing to an outdoor smoking area. The duration of time to be spent in the outdoor smoking area is to be a minimum of 15 mins with a preferable time of 30-60 mins.

Spirometry and Breath Co are to be done for at least 2 to 4 hours prior to exposure and 24 hrs post exposure, at the second visit to the research centre.. At the follow up visit all data will be downloaded and checked and any anomalies will be addressed and clarified with the patient.

National Partners will be trained in the use of devices measuring exposure using AirSpeck and respiratory rate using RESpeck. Data will be transmitted to server at the Centre for Speckled Computing via Internet or mobile phone technology where the data will be analysed.

Subsequently patients in each of 3 countries will be shown how to wear and carry the personal monitor devices , ensuring data is recorded.

Data collection, analysis and report writing: This will be carried out by TFRI in collaboration with Project Partners and in consultation with [name].

Table of tasks

	Baseline visit Minimum of 2 to 4 hrs pre exposure	Post exposure visit Minimum 24hrs post exposure
Consent and information sheet	✓	
Recruitment Questionnaire	✓	
CAT/ACT form	✓	
CO Reading	✓	✓
Spirometry	✓	✓
Training of fitting and use of Respiratory device	✓	
Training and fitting of Particle monitor	✓	
Retrieve equipment and check data recorded		✓
Check patient entries and resolve any data queries		✓
Download data and send to TFRI		✓
Check devices working correctly for next subject		✓

Other support for the Project:

[name]

ELF

Asthma society Ireland

Advisory Panel: Tack Project Partners:

[name]

[name]

[name]

[name] [name]

[name] [name]

[name]

Safety Considerations

The safety of all research participants will be considered at all times, they will be seen in an insured medical practice. All personnel dealing with patients will be fully trained and insured.

The Project will be registered at www.clinicaltrials.com

Data Management and Statistical Analysis:

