All data will be stored on a secure server and will be de-identified. Data will be entered giving each participant a unique identifier code; neither their name, address nor date of birth will be recorded in order to protect the confidentiality of the participant. Analysis will be carried out on a blinded dataset using SPSS. Data will be presented as mean and standard deviation (\pm SD) for continuous variables, or percentage for qualitative variables, as appropriate, or their 95% confidence interval. Differences within groups will be compared with Chi² tests for categorical

variables and Student t test for continuous variables. A p value lower than 0.05 will be considered statistically significant.

Quality Assurance:

Baseline and post exposure data re CO readings, Peak flows any change in medication usage or unscheduled hospital or Dr visits will be entered at source and will be verified by the clinical nurse specialist. Patients will be asked to keep a record of any increase medication usage as well as document any Doctor or Hospital visits as well as description of outdoor smoking area visited. (Appendix 6)

All digitally recorded data will be downloaded from the device to a secure server. A Post Doc and or a Research assistant working with TFRI with advice from partners will further examine study data. Any anomalies found will be addressed and resolved from source data.

Expected Outcomes of the Study

- Exposure levels in the home
- Exposure levels in Smoking areas
- Respiratory symptoms pre and post exposure

Dissemination of Results and Publication Policy:

It is intended that research findings will be published in the form of peer reviewed research articles in first-line high impact or open access journals, and also the presentation of the main results in international tobacco control conferences, such as the European Tobacco or Health Conference, or the Annual or the European Meetings of the Society for Research in Nicotine and Tobacco. There will be a final TackSHS conference in which the main findings will be presented to patients, stakeholders, and policy makers. Together with this, dissemination materials (i.e., factsheets, press releases) will be produced and published in

the TackSHS website as well as disseminated through the websites of the collaborating partners and stakeholders. The results will also be EU deliverables for TackSHS project.

Problems Anticipated:

Recruitment

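### Pre/post spirometry is not matched on bronchodilator timing or time of day, and the visible medication record has no dose time (minor)

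*Combined protocol and SAP*

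**What the plan says.** The Secondary Endpoints list includes "Spirometry pre and post exposure". The population is "30 Asthmatic and 30 Chronic Obstructive Pulmonary Disease (COPD) subjects". Each patient has one test before and one after the outing, and there is no unexposed pair of tests for comparison.

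Timing is set in Patient Schedule: "Spirometry and Breath Co are to be done for at least 2 to 4 hours prior to exposure and 24 hrs post exposure". For the follow-up visit the same section says "The second will be at least 24hrs post exposure to secondhand smoke", and the stay in the smoking area is "a minimum of 15 mins with a preferable time of 30-60 mins". These are lower limits. No upper limit is given for either interval.

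On medication, Quality Assurance lists "Baseline and post exposure data re CO readings, Peak flows any change in medication usage" among the data entered at source and verified by the clinical nurse specialist. It adds: "Patients will be asked to keep a record of any increase medication usage". The Appendix 6 form has a medications field with an amount. It has clock-time fields for the start and end of exposure, for unusual events and for the next appointment, but none for a dose. The Asthma Control Test in Appendix 7 asks about reliever use over the past four weeks and is completed at baseline only.

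For analysis, within-group differences in continuous measures go to a Student t test. The sentence ends "variables and Student t test for continuous variables", and no adjustment is described.

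**The concern.** Many patients with asthma or COPD can be expected to use inhalers, and the plan itself foresees this: it counts increased medication use as a secondary endpoint and asks asthma patients about relievers. FEV1 and FVC depend on how recently a bronchodilator was taken. If the two tests of a pair are done in different bronchodilator states, the difference between them mixes that contrast with any effect of secondhand smoke.

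The error can go either way. A dose closer to the first test produces a fall that looks like a smoke effect. A dose closer to the second test hides a true fall. If mismatches are random across patients they cancel in the mean, but they widen the spread of the differences and cost power in groups of 30. With no unexposed pair of tests, the data offer no internal estimate of this component. Without dose times it cannot be separated exactly afterwards.

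**Working it through.** **1. Gap between the two tests at the stated minimum.** Inputs, all from Patient Schedule: lead L = 2 to 4 h, stay D = 0.25 h (minimum) to 1 h (top of the preferred range), wait P = 24 h. The text does not say whether P runs from the start or the end of exposure, so both are shown.

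- From the start, gap = L + P: 2 + 24 = 26 h to 4 + 24 = 28 h.
- From the end of a 15-minute stay, gap = L + D + P: 2 + 0.25 + 24 = 26.25 h to 4 + 0.25 + 24 = 28.25 h.
- From the end of a 60-minute stay: 2 + 1 + 24 = 27 h to 4 + 1 + 24 = 29 h.

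Clock shift = gap − 24 h: 2 to 4 h, 2.25 to 4.25 h, and 3 to 5 h respectively. Overall the second test falls about 2 to 5 h later in the day. Because the limits are minima, other bookings give other shifts. For example, 4 + 1 + 43 = 48 h is allowed and gives a shift of 0.

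**2. What a clock shift does to time since dose.** Assume, for illustration only, one inhaler dose a day at a fixed hour, and a shift s of 2 to 5 h.

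- If the dose hour precedes both test hours, time since dose is s longer at the second test, that is 2 to 5 h longer.
- If the dose hour lies between the two test hours, the change is s − 24: 2 − 24 = −22 h to 5 − 24 = −19 h, so the second test is much closer to a dose.

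The same schedule can therefore push the comparison in opposite directions in different patients. As-needed reliever doses follow no fixed hour and may add to this.

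**3. Effect on a group mean.** Let k be the net number of patients more recently dosed at one test than at the other, and R their mean bronchodilator response. Shift in mean change = (k/30) × R.

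- k = 1: 1/30 = 3.3% of R.
- k = 3: 3/30 = 10% of R.
- k = 0: no shift in the mean, only added variance.

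The documents give neither k nor R, so no value in mL follows.

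**4. Sensitivity of the test to a one-directional shift (assumption, not estimate).** Take a two-sided paired t test at 0.05 with n = 30, no smoke effect, and a systematic shift of b SDs of the paired difference. It rejects in 8.3% of studies at b = 0.1, 18.5% at 0.2 and 35.5% at 0.3. Nothing in the documents fixes b. It is 0 if mismatches balance. The plan states neither sidedness nor pairing; both are assumed here.

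**5. What the visible records could recover.**

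| Item | Visible source | Time of a routine dose? |
|---|---|---|
| Drug and amount | Appendix 6 | No |
| Change or increase in use | Quality Assurance | No |
| Unusual event, with time | Appendix 6 | Only if a reliever dose is tied to an event |
| Reliever use over four weeks | Appendix 7, baseline, asthma only | No |

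Pairs with a change in medication could be separated from the rest. Exact time since dose could not be reconstructed.

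**The case against.** The strongest objection concerns the records. A reader might infer from Appendix 6, which has only a date for the baseline visit, that the clock time of spirometry is never recorded. The documents do not support that. Appendix 6 describes the outing and, as extracted, holds no spirometry or CO results. Quality Assurance says clinical readings are entered at source, and that source record is not shown. The sensors are fitted and retrieved at the same two visits and produce time-stamped data (RESpeck section and Appendix 5), so visit times might be approximated if recording spans both visits. Whether the spirometer stores a time is not stated. This objection stands, and the point is confined to dose time and matching.

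A reader might also infer that no correction could be made afterwards. That is too strong. Changes in medication are recorded and verified, and patient entries are checked at the second visit, so a coarse split is possible. What is lost is exact dose timing: a routine dose is not an anomaly to be queried, and the dose before baseline would have to be recalled from at least 26 h earlier.

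The patient information sheet (Appendix 1) was not available and could contain an inhaler instruction, one item of the recruitment questionnaire is broken, and Appendix 6 is a flattened table. A site spirometry procedure could also cover dose timing. These limits restrict the finding to the visible text. They do not supply a rule or a field.

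Finally, this is a secondary endpoint in a study with no intervention beyond monitoring, and no size of bias is shown. That stands and sets the grade.

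**Conclusion.** The point holds in a limited form. In the visible text, the two spirometry tests are tied only to exposure, are not matched on time since the last bronchodilator or on time of day, and are accompanied by a medication record without dose times. At the minimum schedule the second test is about 2 to 5 h later in the day; other bookings can give any shift, including none.

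The consequence is avoidable noise, and possible bias in either direction, in the within-group FEV1/FVC comparison. Its size and direction are unknown. A reader might infer that the spirometry result will be biased towards a smoke effect, or that the false-positive rate is raised by a known amount. Neither follows: both would need a net mismatch in one direction, which the documents neither show nor exclude.

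The conclusion assumes that some patients use bronchodilators and that the unavailable pages hold no matching rule. Severity: minor, worth considering.

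**What to change.** 1. At both spirometry visits, record the drug, amount and clock time of the last respiratory medicine. Add the time of the test if the source record does not already hold it.
2. Add a time column beside the medication and amount entries in Appendix 6.
3. Where feasible, book the two tests at a similar interval after the patient's usual inhaler and at a similar time of day. Do not withhold or change treatment.
4. Keep every pair in the main spirometry result. Add a sensitivity analysis that splits pairs by same or different bronchodilator state, with the rule for same fixed before analysis. State that reliever use after exposure may itself be an effect of secondhand smoke, so the split is descriptive and does not replace the main result.

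The cost is a few form fields and slightly less flexible booking. No new procedure is needed.

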Appendix 2:

Recruitment Questionnaire

Tackling secondhand tobacco smoke and e-cigarette emissions: **exposure assessment**, novel interventions, impact on lung diseases and economic burden in diverse European populations. The TackSHS Project.

New approaches to monitoring exposure to air pollution and health effects

Researcher: [name]

This is a short questionnaire to ascertain personal smoking status, other sources of exposure, average weekly exposure in hospitality premises, and experience of respiratory symptoms. Please circle your response where appropriate.

Unique Identifier code: XXXX

1. Are you Male Female
2. What is your age?
3. Do you ever smoke cigarettes/tobacco? Yes/No

If yes

- for how many years?
- At what age did you start to smoke?
- Do you smoke everyday Yes/No
- How many do you smoke on an average per day?

4. Do you currently live with any smokers? Yes/No

4. Do you currently live with any smokers? Yes/No

If yes

- how many?
- do they smoke in the home?

5. Are you exposed to smoking in cars? Yes/No

If yes

- How many trips per week?
- What is the average duration of these trips?

6. Do you visit smoking areas in the hospitality sector such as Pubs or Restaurants?

Yes/No

If yes:

- How often per month?

Neither

If yes how long is it since your diagnosis? -----Years -----Months

8. Do you suffer from any of the following?

Wheeze	Never	Sometimes	Often
Cough	Never	Sometimes	Often

Shortness of breath	Never	Sometimes	Often
Stinging or irritation of the eyes	Never	Sometimes	Often

Appendix 3:

CO Monitor

All the tools you need for smoking cessation... from CareFusion

At CareFusion we are proud of our innovations and dedication to providing healthcare professionals with the best tools for the job.

As someone who is involved in the field of smoking cessation, you are only too well aware of the dangers caused by smoking. What you need is a means of quickly and effectively monitoring your patient's breath Carbon Monoxide levels, and then convincingly persuading them of the risks they bring upon themselves by smoking.

Design Innovation

Ergonomically designed unit of distinctive appearance, the textured handgrip encourages easy and reassuring use. Both the MicroCO™ and SmokeCheck™ are small, lightweight and are moulded from high impact ABS for durability.

CareFusion can offer you two types of carbon monoxide monitor:

MicroCO™

The MicroCO™ provides accuracy and simplicity in CO breath testing. Some of its many features include, fast response time, 1ppm resolution, immediate display of CO levels in PPM and %COHB, colour light indicators, capable of interfacing with COBRA™, (a complimentary Windows® based software package for performing and storing real time breath tests on your PC).

SmokeCheck™

The SmokeCheck™ is designed as a simple screening test for cigarette consumption. Giving an instant indication of breath CO breath ranges (expressed in PPM), and backed up with colour light indicators.

Conversion of PPM results to %COHB is easily done using the SmokeCheck™'s smoking cessation guide chart provided.

Complete with all accessories

Both MicroCO™ and SmokeCheck™ come complete with a hard shell carry case, sample cardboard mouthpieces, one-way plastic mouthpiece adaptor, calibration adaptor, calibration tool, 9V PP3 battery and operating manual.

Customer Benefits and Features of the MicroCO™

The MicroCO™ is a powerful diagnostic tool for measuring alveolar Carbon Monoxide concentrations (in PPM) and percentage Carboxy haemoglobin. Operating from a single 9V PP3 battery for approximately 2000 tests the MicroCO™ combines accuracy and simplicity making it the perfect choice for professionals worldwide.

Ease of Use

Measurements are easily obtained from a single expiration and are aided by an auto-zero function at turn on, combined with a breath hold countdown timer. The results are then instantly displayed on the large, easy to read liquid crystal display, and are visually represented by the appropriate colour light indicator.

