Patients will be contacted through ELF national organisation with input from national/project partners. Inclusion and exclusion criteria, Information sheet and a short recruitment questionnaire (Appendix 1 and 2) will be distributed to possible patient volunteers.

Consent:

Once eligibility has been determined patients will be given an appointment (in a research room either Clinic/Hospital or University based, venue to be confirmed) where they will receive an information leaflet. Once this has been read and any concerns of the participant addressed and explained, they will then be asked to provide written consent prior to their study enrolment. Consent will be obtained from all participants. Consent is on-going and participants can revoke consent at any stage of the project. (Appendix 1)

Technicians and researchers will be trained in the use of monitoring devices by TFRI staff. The 60 patients will be fitted with equipment which will measure their exposure to pollutants including Secondhand smoke as well as measuring the effects on their breathing rate.

Devices used to gather data:

Carefusion CO Monitor

The CO Monitor features single-button operation and coloured light indicators to simplify patient understanding of the process: (Appendix 3)

- Green: 0 to 6ppm
- Amber: 7 to 10ppm
- Red: 11 to 20ppm
- Flashing red and alarm: >20ppm

Spirometer:

Spirometry measures the volume of air that the patient is able to expel from the lungs after maximal inspiration.

Spirometry is invaluable as a screening test of general respiratory health, similar to BP measurement in cardiovascular disease. It is a reliable method of diagnosing and differentiating between obstructive airways disorders (e.g. COPD, asthma) and restrictive diseases (where the size of the lung is reduced, e.g. fibrotic lung disease).

Spirometry can also be used to determine the severity of asthma and COPD. This is important because the severity of these diseases cannot be predicted simply from the clinical signs and symptoms. The FEV₁ is the maximal volume of air exhaled in the first second of a forced expiration from a position of full inspiration (expressed in litres at BTPS). The forced vital capacity (FVC) is the maximal volume of air exhaled with maximally forced effort from a maximal inspiration (expressed in litres at body temperature and ambient pressure saturated with water vapour – BTPS).

RESpeck:

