The second monitor was the RESpeck RR sensor (University of Edinburgh Department of Speckled Computing, School of Informatics, Scotland), which was an encapsulated tri-axial accelerometer positioned on the left side of the abdomen just under the costal margin. RESpeck recorded changes in abdominal position in three orthogonal axes, relative to gravity. These data were automatically integrated and differentiated into a derived ‘activity’ signal, and a RR signal with a shape similar to inspiratory and expiratory flow. RESpeck had been verified to be a reliable measure of RR when compared with RR derived from a nasal cannula in anaesthetised post-operative patients; instantaneous RESpeck RR matched the routine clinical measurement of RR within two breaths per minute (bpm)—an acceptable limit of accuracy employed previously—on 86 % of occasions, with a mean absolute difference of 0.6 bpm [15]. However, our study was the first time that RESpeck had been implemented in the pre-hospital environment. RESpeck was entirely wireless and all data were transmitted using a Bluetooth 4.0 Low-Energy protocol to an iPod (Apple, Cupertino, CA, USA) on which the data were displayed and recorded. Accelerometer data were recorded at a rate of 12.5 Hz. Figure 2 displays both

medical sensors and their method of attachment to the body.

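### The visit 1 breath CO result is not kept from the participant, and own smoking between the two readings is not recorded, so a current smoker's reaction to the reading could bias the pre/post CO change.

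*Combined protocol and SAP*

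**What the plan says.** The Secondary Endpoints list "Breath Carbon Monoxide (CO) monitoring pre and post study". Under Patient Schedule and in the Table of tasks, CO is read at the baseline visit, at least 2 to 4 hours before exposure, and again at least 24 hours after it.

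The device section of the protocol states: "The CO Monitor features single-button operation and coloured light indicators to simplify patient understanding of the process". It then gives the bands: green 0 to 6 ppm, amber 7 to 10, red 11 to 20, and finally "Flashing red and alarm: >20ppm". Appendix 3 reprints the maker's brochure, which is addressed to smoking-cessation professionals and offers the device for measuring patients' CO "and then convincingly persuading them of the risks they bring upon themselves by smoking". It says that the result appears at once on a large display and as a colour.

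The COPD inclusion criteria admit current as well as ex-smokers, and the asthma criteria do not mention smoking. Under Ethics the plan says "there will be no intervention other than monitoring". The Rationale, discussing PM2.5 feedback and occupational hazards, says that feeding back measured exposure can motivate people to change their behaviour.

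Own smoking is asked once, as an average per day, in the Recruitment Questionnaire (Appendix 2). The Appendix 6 form covers exposure times, walls, smokers and e-cigarette users present, unusual events and medications. It does not ask about the participant's own cigarettes. The analysis section plans a Student t test within groups at 0.05, with no adjustment for smoking.

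**The concern.** For a current smoker, own smoking is a source of breath CO separate from secondhand smoke. If the first reading is shown as a red light, or sets off the alarm, it comes between the two measurements whose difference is the endpoint. A participant who reacts by smoking less lowers the second reading for a reason unrelated to the smoking area visited.

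The design could not reveal this. There is no unexposed group whose CO would show the same reaction, and no record of own cigarettes between the readings. The blinding that is mentioned applies to the dataset at analysis and not to participants. A fall caused by reaction to the display could not be separated from an exposure effect, and any CO rise still present at visit 2 could be masked.

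**Working it through.** The plan gives no sample-size calculation, expected CO change or standard deviation, so there is no stated figure to reproduce. The check has two parts.

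**1. Whether the route exists in the documents**

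- *Patient-facing display:* yes, in the protocol's device section and not only in the brochure.
- *Participants who could react:* current smokers, who are eligible in the COPD group and not excluded from the asthma group. Readings of 0 to 6 ppm show green, so the warning colours concern people with raised CO. A non-smoker has no own smoking to change.
- *Time to react:* at least 2 + 24 = 26 to 4 + 24 = 28 hours between readings, with no stated maximum.
- *Safeguard:* none found in the text available. The patient information sheet and consent form (Appendix 1), and part of the text after the brochure, could not be checked.

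**2. An illustration of size**

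Bias in mean change = −(share of current smokers) × (relative cut in their CO) × (their mean baseline CO).

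From the protocol: 30 participants per disease group, and the ends of the red band (11 and 20 ppm) as the smokers' mean CO. Using that band as the mean is an assumption. So are the smoker share, the relative cut and the SD of change.

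| Share of current smokers | Cut of 5% to 20%, mean 11 ppm | Cut of 5% to 20%, mean 20 ppm |
|---|---|---|
| 0% | 0 | 0 |
| 25% | −0.14 to −0.55 ppm | −0.25 to −1.0 ppm |
| 50% | −0.28 to −1.1 ppm | −0.5 to −2.0 ppm |
| 100% | −0.55 to −2.2 ppm | −1.0 to −4.0 ppm |

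Example: 0.5 × 0.10 × 11 = 0.55 ppm, and 0.5 × 0.10 × 20 = 1.0 ppm.

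These two values were put into a two-sided paired t test (noncentral t, alpha 0.05, n = 30) with no true exposure effect. The plan states neither pairing nor sidedness, so both are assumed. The chance of a significant result, almost always a fall, is:

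- SD of change 3 ppm: 16% (bias 0.55) to 42% (bias 1.0)
- SD of change 5 ppm: 9% (bias 0.55) to 19% (bias 1.0)

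The nominal rate is 5%. With 25% smokers, a 5% cut and a mean of 11 ppm, the rate is barely affected: 5.7% at SD 3 and 5.2% at SD 5. The illustration shows that the effect could be trivial or material, and the documents do not say which.

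**The case against.** The case against is substantial, and several parts of it stand.

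- *The brochure is not the protocol.* Correct. The Table of tasks lists a CO reading with no counselling step. A reader might infer that the study uses the monitor to persuade participants, or that it contradicts its own statement about no intervention. The documents support neither: taking a reading is monitoring, and no text says that staff will use the result to counsel. The concern rests on the device section, which describes a display meant for the patient without saying whether participants are shown their result.
- *There is no evidence that one reading changes smoking within about a day.* Correct. The Rationale's remarks concern other kinds of feedback, so they make the mechanism plausible and give it no size. Direction is not certain either: a smoker shown green or amber may be reassured. Nor do the documents say whether a CO rise from secondhand smoke would persist 24 hours later.
- *Only one secondary endpoint and only current smokers are affected.* Correct.
- *Turning the display away does not silence the alarm above 20 ppm.* Correct, so masking alone is not enough.
- *Own smoking can vary between visits for any reason.* Also correct. Reaction to the display is one route into that wider gap.

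A reader might extend the point to respiratory rate, a primary endpoint, because Appendix 4 says the RESpeck data went to an iPod "on which the data were displayed and recorded". That sentence belongs to a reprinted ambulance study in which a researcher started and stopped the recordings. For this study the protocol says only that files will be downloaded from the iPod or tablet. Nothing says that participants see a breathing trace, so the extension is not supported.

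**Conclusion.** The point holds for breath CO, as a possible bias. The display is described as patient-facing, current smokers may enrol, and the available text neither withholds the first reading nor records own smoking between visits. The planned comparison has no control group and no adjustment. A reaction to the reading could therefore bias the CO change, probably downward, and the data as planned could not show it.

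The size is unknown. It is zero without current smokers. The ppm shifts and error rates above depend on an assumed smoker share, relative cut, baseline CO and SD of change, and should not be quoted as estimates. The primary endpoints are not affected by this route. The finding is also conditional on Appendix 1, which could not be checked. This calls for a cheap improvement to a secondary endpoint and does not threaten the study as a whole.

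**What to change.** 1. In the CO monitor section and the Patient Schedule, state that at visit 1 staff read and record the ppm value with the screen and lights out of the participant's view. Both results are given after the visit 2 reading. Staff still see every value, so how they handle a high one is unchanged. The information sheet should tell participants when they will receive their results, so that they remain fully informed.
2. Because the alarm cannot be hidden in this way, record at both readings the participant's own cigarettes (since visit 1, for the second reading) and the time since the last cigarette. Appendix 6 or the visit form could carry these items.
3. In the analysis section, report CO change separately for current smokers and non-smokers.

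Appendix 3 describes two monitor models, and a 1 ppm resolution is stated for only one. The plan should name the model used, because step 1 needs a numeric reading.

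The cost is a line in the visit instructions, one or two form items and a wait until visit 2 for the participant's result. Steps 2 and 3 also cover changes in own smoking that have nothing to do with the display.
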